### **12.2 Deviations from the Protocol**

If deviations from the protocol occur, the investigator must inform the monitor, and the implications of the deviation must be reviewed and discussed. Any deviation must be documented, either as answer to a query in the e-CRF, in a protocol deviation report or a combination of both. A log of protocol deviation reports will be maintained by Ferring. Protocol deviation reports and supporting documentation must be kept in the Investigator's File and in the Trial Master File.

### **12.3 Premature Trial Termination**

Both the investigator (with regard to his/her participation) and Ferring reserve the right to terminate the trial at any time. Should this become necessary, the procedures will be agreed upon after consultation between the two parties. In terminating the trial, Ferring and the investigator will ensure that adequate consideration is given to the protection of the best interests of the subjects. Regulatory authorities and the IEC/IRB will be informed.

## **13 REPORTING AND PUBLICATION**

### **13.1 Clinical Trial Report**

The data and information collected during this trial will be reported in a clinical trial report prepared by Ferring and submitted for comments and signature to the signatory investigator.

### **13.2 Confidentiality and Ownership of Trial Data**

Any confidential information relating to the IMP or the trial, including any data and results from the trial will be the exclusive property of Ferring. The investigator and any other persons involved in the trial will protect the confidentiality of this proprietary information belonging to Ferring.

### **13.3 Publication and Public Disclosure**

#### **13.3.1 Publication Policy**

At the end of the trial, one or more manuscripts for joint publication may be prepared in collaboration between the investigator offered authorship and Ferring.

Any external contract research organisation or laboratory involved in the conduct of this trial has no publication rights regarding this trial.

#### **13.3.2 Public Disclosure Policy**

It is the responsibility of Ferring to register the trial in an appropriate registry, i.e. at [www.cde.org.cn](http://www.cde.org.cn), which is designated by the China Food and Drug Administration (CFDA).

## 14 ETHICAL AND REGULATORY ASPECTS

### 14.1 Independent Ethics Committee (IEC) or Institutional Review Board (IRB)

An IEC/IRB will review the protocol and any amendments and advertisements used for recruitment. The IEC/IRB will review the Subject Information Sheet and the Informed Consent Form, their updates (if any), and any written materials given to the subjects. The IEC/IRB, to which the protocol has been submitted, and the name of the committee chairman will be denoted in the clinical trial report.

### 14.2 Regulatory Authority Authorisation / Approval / Notification

The regulatory permission to perform the trial will be obtained in accordance with applicable regulatory requirements. All ethical and regulatory approvals must be available before a subject is exposed to any trial-related procedure, including screening tests for eligibility.

### 14.3 End-of-Trial Notification

End-of-trial notification will be reported according to local regulations. In addition, a summary of the clinical trial report, e.g. the synopsis, will be provided when available and within one year of the trial completion (last subject last visit).

### 14.4 Ethical Conduct of the Trial

This trial will be conducted in accordance with the ethical principles that have their origins in the Declaration of Helsinki, in compliance with the approved protocol, ICH-GCP and applicable regulatory requirements.

### 14.5 Subject Information and Consent

The investigator (or the person delegated by the investigator) will obtain a freely given written consent from each subject after an appropriate explanation of the aims, methods, anticipated benefits, potential hazards, and any other aspects of the trial which are relevant to the subject's decision to participate. The trial subject must be given ample time to consider participation in the trial, before the consent is obtained. The Informed Consent Form must be signed and dated by the subject and the investigator who has provided information to the subject regarding the trial before the subject is exposed to any trial-related procedure, including screening tests for eligibility.

The investigator (or the person delegated by the investigator) will explain that the subject is free to completely refuse to enter the trial or to withdraw from it at any time, without any consequences for his/her further care and without the need to justify his/her decision.

The subject will receive a copy of the Subject Information and his/her signed Informed Consent Form.

### 14.6 Subject Participation Card

The subject will be provided with a Subject Information Card bearing the following information:

- That she is participating in a clinical trial

- That she is treated with FE 999049
- The name and phone number of the investigator
- Name and address of Ferring (if required by local regulations)

The subject will be asked to return the Subject Information Card at the last trial visit, if applicable.

Additionally, each subject's primary care physician will be notified of their participation in the trial by the investigator, if the subject agrees and if applicable.

#### **14.7 Compliance Reference Documents**

The Declaration of Helsinki, the consolidated ICH-GCP, and the CFDA regulations and other national law(s) in the country where the trial takes place shall constitute the main reference guidelines for ethical and regulatory conduct.

## **15 LIABILITIES AND INSURANCE**

### **15.1 ICH-GCP Responsibilities**

The responsibilities of Ferring, the monitor and the investigator will be as defined in the ICH-GCP consolidated guideline, and applicable regulatory requirements in the country where the trial takes place. The investigator is responsible for adhering to the ICH-GCP responsibilities of investigators, for dispensing the IMP in accordance with the approved protocol or an approved amendment, and for its secure storage and safe handling throughout the trial.

### **15.2 Liabilities and Insurance**

Ferring is, as sponsor, responsible for ensuring appropriate general/product liability insurance and, as required in accordance with applicable laws and regulations, country-specific liability insurance coverage for claims made by a trial subject for injury arising from the subject's participation in the trial.

## 16 ARCHIVING

### 16.1 Investigator File

The investigator is responsible for maintaining all the records, which enable the conduct of the trial at the site to be fully understood, in compliance with the ICH-GCP. The trial documentation including all the relevant correspondence should be kept by the investigator for at least 15 years after the completion or discontinuation of the trial, if no further instructions are given by Ferring.

The investigator is responsible for the completion and maintenance of the confidential subject identification code which provides the sole link between named subject source records and anonymous e-CRF data for Ferring. The investigator must arrange for the retention of this Subject Identification Log and signed Informed Consent Form for at least 15 years after the completion or discontinuation of the trial.

No trial site document may be destroyed without prior written agreement between the investigator and Ferring. Should the investigator elect to assign the trial documents to another party, or move them to another location, the Ferring must be notified. If the investigator retires and the documents can no longer be archived by the site, Ferring can arrange having the Investigator File archived at an external archive.

### 16.2 Trial Master File

Ferring will archive the trial master file in accordance with ICH-GCP and applicable regulatory requirements.

1.1 Definitions/ Abbreviations

1.1.1 Definition of Terms

Terms	Definitions
Prior medication	Medication taken prior to treatment (i.e. the stop date is before the first IMP administration)
Concomitant medication	Medication that is not stopped before the first IMP administration, or is started between IMP administration and the follow-up visit (visit 13)
Post-treatment medication	Medication with start date after the follow-up visit (visit 13)
Pre-treatment Adverse Event	An Adverse Event with start time after signing of informed consent and before administration of IMP
Treatment Emergent Adverse Event	An Adverse Event that has start time or worsens in intensity after administration of IMP until the follow-up visit (visit 13)
Post-treatment Adverse Event	An Adverse Event that has start time after the follow-up visit (visit 13)
AUC	Area under the concentration-time curve from dosing to infinity
AUC_t	Area under the concentration-time curve from dosing up to time t, where t is the last time point at which the concentration is above the lower limit of quantification.
% Extrap AUC	Percentage of AUC that is due to extrapolation from the last measurable concentration
CL/F	Apparent total systemic clearance
C_{max}	Maximum concentration observed
λ_z	First-order rate constant associated with the terminal (log-linear) portion of the concentration-time curve
NCA	Non-compartmental analysis
t_½	Terminal elimination half-life
t_{max}	Time of maximum observed concentration (C _{max})
V_{z/F}	Apparent volume of distribution associated with the terminal phase

1.1.2 Abbreviations

Abbreviations	Meaning of abbreviations in document
AE	Adverse Event
ADR	Adverse Drug Reaction
ATC	Anatomic Therapeutic Chemical
CV	Coefficient of Variation
ECG	Electrocardiogram
FAS	Full Analysis Set
HLGT	High Level Group Term
HLT	High Level Term
IMP	Investigational Medicinal Product

LLQ	Lower Limit of Quantification
MedDRA	Medical Dictionary for Regulatory Activities
NIMP	Non-investigational Medicinal Product
PK	Pharmacokinetic
PP	Per Protocol
PT	Preferred Term
SAE	Serious Adverse Event
SOC	System Organ Class
TEAE	Treatment Emergent Adverse Event

1.2 Presentation of results

1.2.1 Presentation of descriptive results

Categorical data will be summarised using frequency (n) and relative frequency as percentage (i.e. n/N*100).

Continuous data will be summarised using the number of subjects (N), mean and standard deviation (SD), median and range (minimum to maximum). For PK parameters the descriptive statistics will additionally include the geometric mean and the CV. For $t_{1/2}$, the harmonic mean will be included in addition to the geometric mean. For t_{max} the geometric mean and the CV will be omitted.

1.2.2 Presentation of inferential results

Inferential results will be presented using point estimates, two-sided 95% confidence intervals, and two-sided p-values.

1.2.3 Subject data listings by domain

All subject data will be presented in listings organised in accordance with the ICH E3 guideline.

2 Trial Objectives and Endpoints

2.1 Objectives

The objectives of the trial are to:

- Investigate the single-dose pharmacokinetics of FE 999049 administered as a subcutaneous abdominal injection in healthy Chinese women
- Investigate the safety and tolerability of a single dose of FE 999049 administered as a subcutaneous abdominal injection in healthy Chinese women

2.2 Endpoints

- Pharmacokinetics (AUC, AU_{Ct}, C_{max}, t_{max}, CL/F, V_z/F, t_{1/2})
- Safety (ECG, vital signs, laboratory parameters, adverse events)
- Injection site reactions
- Presence of anti-FSH antibodies

3 Trial design

3.1 General Design Considerations

This is an open-label, randomised parallel group trial investigating the pharmacokinetics of a single subcutaneous abdominal injection of FE 999049. Subjects will be randomised to 3 dose groups with 8 healthy Chinese women in each group.

After testing negative in pregnancy tests, the subjects will receive two subcutaneous administrations of a 1-month depot formulation of the GnRH agonist DECAPEPTYL Depot 3.75 mg to down-regulate endogenous release of FSH during the trial. The first DECAPEPTYL Depot administration will be given 28 ± 1 days prior to the first dose of IMP. In women not receiving hormonal contraceptives, the first DECAPEPTYL Depot administration should take place in the time interval 7 days before to 3 days after the expected start of menstruation. In women discontinuing combined oral contraceptives, the first DECAPEPTYL Depot administration should take place after the subjects have discontinued the hormonal contraception and within 5 days of commencement of bleeding. A second administration will be given 10 ± 1 days prior to the first IMP administration.

To verify low stable endogenous hormones, serum FSH will be measured at Day -3 and Day -1. If any of the measurements is >5 mIU/mL, the subject will be excluded.

The doses to be administered are 12, 18, and 24 μ g at a concentration of 33.3 μ g/mL. For each subject the treatment period is 10 days, and the total duration of the trial from screening to the last follow-up visit after treatment will not exceed 13 weeks.

3.1.1 Sample Size

No formal sample size calculation has been performed for this phase 1 trial. Eight subjects receiving active treatment in each dose panel is considered sufficient to provide adequate information about the pharmacokinetic parameters at each dose level for the purposes of this trial.

3.1.2 Visits

The trial comprises 14 visits. Visit 1 is a screening visit and visits 2-5 belong to the run-in period. Visit 5 is the end of the run-in period and the start of the treatment period. It starts the day before IMP administration and ends two days after IMP administration. During this time the subjects are residential at the clinic. At visits 6-12 the subjects come to the clinic in the morning for PK serum sampling. Visit 13 is a follow-up visit that takes place the day after the last PK sample was taken (10 days after IMP administration). This visit is regarded as the end of the treatment period. Visit 14 takes place 27 days after IMP administration and has the purpose of collecting blood samples for assessment of the presence of anti-FSH antibodies. The sequence and timing of trial events are shown in Figure 1.

[figure not shown]

Figure 1 Sequence and timing of trial events

4 Protocol Violations

Major protocol violations, such as significant non-compliance or other serious unforeseen violations deemed to invalidate the data collected for the purpose of the trial will lead to exclusion of the data from analysis. In case of minor protocol violations, data will not be excluded from the data analysis. The rating of protocol violations in ‘minor’ and ‘major’ will be decided based on a review of the data before declaration of ‘clean file’ and lock of database.

5 Analysis sets

5.1 Full Analysis Set

The full analysis set (FAS) includes data from all dosed subjects. The FAS will be used for presentation of compliance and all baseline characteristics (demographics, medical history, prior and concomitant medication). Subjects will be analysed according to the actual treatment received.

5.2 Per Protocol Analysis Set

The per protocol (PP) analysis set includes data from all dosed subjects except data excluded because of major protocol violations as discussed in Section 4. The PP analysis set will be used for presentation of PK data. Subjects will be analysed according to the actual treatment received.

5.3 Safety Analysis Set

The safety analysis set includes data from all dosed subjects and will be used for safety analysis. Subjects will be analysed according to the actual treatment received. The safety analysis set will be identical to the FAS.

6 Trial population

6.1 Demographics and Other Baseline Characteristics

Descriptive statistics of demographics and other baseline characteristics (e.g. FSH for eligibility determination) will be presented by dose group and in total.

6.2 Medical History

Medical history recorded at the screening visit will be coded using MedDRA and summarised by dose group and in total. The version of MedDRA will be documented.

6.3 Prior and Concomitant medication

Prior and concomitant medication will be summarised by ATC classification (1st and 2nd level). Medications will be tabulated separately for:

- Prior medication; i.e. medication taken exclusively prior to treatment (i.e. the stop date is before the first IMP administration)
- Concomitant medication; i.e. medication that is not stopped before the first IMP administration or is started between IMP administration and the follow-up visit (visit 13). If the timing of the dose of a concomitant medication cannot be established in relation to the administration of IMP, it will be considered as concomitant medication.
- Post-treatment medication; i.e. medication with start date after the follow-up visit (visit 13).

7 Subject Disposition

All post randomisation discontinuations will be summarised by time of and reason for discontinuation. The number of subjects screened but not found eligible will be stated in the trial report, and the reason for screening failure will be summarised.

8 Exposure and Treatment Compliance

Times for administration of NIMP and IMP will be listed. Potential non-compliances with NIMP or IMP administration will be listed.

9 Pharmacokinetics

9.1 General considerations

All individual concentration data (both baseline adjusted and unadjusted) and PK parameters will be listed by treatment and summarised by treatment with descriptive statistics. Individual and mean serum concentration (both baseline adjusted and unadjusted) vs. time curves will be presented for each treatment both on linear and logarithmic concentration axes.

For serum concentrations the descriptive statistics will include number of subjects, arithmetic mean, standard deviation, median, minimal value and maximal value. For PK parameters the descriptive statistics will additionally include the geometric mean and the between-subject CV (i.e. the coefficient of variation based on the total variability, calculated as $100 \cdot \sqrt{e^{s^2} - 1}$, where s is the standard deviation calculated for the log-transformed data).

9.1.1 Pharmacokinetic Endpoints

The calculation of PK parameters will be performed by Department of Translational Medicine, Ferring Pharmaceuticals. The PK parameters will be calculated for non-corrected as well as baseline corrected data by non-compartmental analysis (NCA) using the software Phoenix WinNonlin® (Certara, US). The baseline value is the mean of the three values obtained prior to the administration of the IMP (-1h, -30 min, 0 min). Baseline corrected values below LLQ will be set to zero. Actual sampling time points relative to dosing will be used for the NCA and on the individual plots of serum concentration versus time. Serum concentration values below lower limit of quantification (LLQ) and missing values (e.g. no blood sample collected or no value obtained at analysis) will be excluded from the estimation of λ_z . Values below LLQ will be represented as LLQ/2 in the plots and in descriptive statistics.

PK parameters will be estimated based on measurements from Day 1 to Day 10. From the serum concentration-time data of FE 999049 the following parameters will be estimated: AUC, AUC_t, % Extrap AUC, C_{max}, t_{max}, λ_z , t_{1/2}, CL/F, and V_z/F.

Selection of data points for calculation of t_{1/2} via λ_z will be based on the following considerations:

- The automatic range selection used in Phoenix WinNonlin® will be used to propose an optimal number of time points to use for the calculation of λ_z .
- The time range of samples used to estimate λ_z should preferably exceed the derived terminal half-life t_{1/2} ($= \ln 2/\lambda_z$).
- All the samples used to calculate λ_z should ideally fall in the log-linear terminal phase.
- At least three samples above LLQ obtained during the log-linear terminal phase will if possible be included in the calculation of the λ_z .

- The final selection of samples for calculation of λ_z will be based on visual inspection of log-concentration-time plots of individual profiles.

AUC will be calculated by the linear trapezoidal method. PK parameters will be summarised by treatment (i.e. dose group) using descriptive statistics.

Dose proportionality will be investigated for each of AUC and C_{max} using a multiplicative analysis of variance model (i.e. AUC and C_{max} will be log-transformed before analysis) with log(dose) as covariate. In this model, a covariate coefficient of 1 would indicate dose proportionality.

10 Safety

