### **3.5.6 Withdrawal Criteria**

In order to ensure down-regulation and minimise any interference from endogenous FSH, any subject that does not have a FSH concentration  $\leq 5$  IU/L on Day -3 and Day -1 will be withdrawn from the trial before randomisation. The Day -3 assessment may be repeated up to 5 days later if the first FSH measurement is  $> 5$  IU/L (subsequent visits will be postponed accordingly). The second assessment and the Day -1 assessment must be within acceptable ranges. No other specific withdrawal criteria are defined.

Since this trial comprises a single subcutaneous injection, no specific withdrawal criteria are defined that will arrest the treatment.

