### 9.7.2 Endpoints

#### 9.7.2.1 Pharmacokinetics

The statistical analysis of PK will be performed by Department of Translational Medicine, Ferring Pharmaceuticals. The PK parameters will be calculated for non-corrected as well as baseline corrected data by non-compartmental analysis (NCA) using the software Phoenix WinNonlin® (Certara, US). The baseline value is the mean of the values obtained prior to the administration of the IMP. Actual sampling time points relative to dosing will be used for the NCA and on the individual plots of serum concentration versus time. Serum concentration values below lower limit of quantification (LLQ) and missing values (e.g. no blood sample collected or no value obtained at analysis) will be excluded from the NCA. Values below LLQ will be represented as LLQ/2 in the plots.

PK parameters will be estimated based on measurements from Day 1 to Day 10. From the serum concentration-time data of FE 999049 the following parameters will be estimated, if possible: AUC, AUCt, % Extrap AUC, Cmax, tmax, λz, t1/2, CL/F, and Vz/F.

Selection of data points for calculation of t1/2 via λz will be based on the following considerations:

- The automatic range selection used in Phoenix WinNonlin® will be used to propose an optimal number of time points to use for the calculation of λz.

- The time range of samples used to estimate  $\lambda_z$  should preferably exceed the derived terminal half-life  $t_{1/2}$  ( $= \ln 2/\lambda_z$ ).
- All the samples used to calculate  $\lambda_z$  should ideally fall in the log-linear elimination phase.
- At least three samples above LLQ obtained during the log-linear elimination phase will if possible be included in the calculation of the  $\lambda_z$ .
- The final selection of samples for calculation of  $\lambda_z$  will be based on visual inspection of log-concentration-time plots of individual profiles.

AUC will be calculated by the linear trapezoidal method. PK parameters will be presented by dose with number of measurements, number of missing data, mean, standard deviation, median, minimum, maximum, geometric mean, and %CV (based on untransformed data) for geometric mean (for AUC and  $C_{max}$ ). For  $t_{1/2}$ , the harmonic mean will be listed in addition to the geometric mean. For  $t_{max}$  the geometric mean and the %CV will be omitted.

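### Does the lack of a rule for pre-dose FSH values below LLQ in the baseline mean call for a change to the SAP?

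*SAP*

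**What the plan says.** Both documents calculate the PK parameters twice, on uncorrected and on baseline-corrected concentrations. Protocol 9.7.2.1 defines the baseline thus: "The baseline value is the mean of the values obtained prior to the administration of the IMP". SAP 9.1.1 adds the number and timing of the samples: "The baseline value is the mean of the three values obtained prior to the administration of the IMP (-1h, -30 min, 0 min".

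Values below LLQ are treated in three ways:

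- **Exclusion.** In the protocol, values below LLQ and missing values (the latter including "no value obtained at analysis) will be excluded from the NCA"). In the SAP the same sentence ends differently: "no value obtained at analysis) will be excluded from the estimation of" λz.
- **Zero**, in the SAP only: "Baseline corrected values below LLQ will be set to zero".
- **LLQ/2.** Protocol: "Values below LLQ will be represented as LLQ/2 in the plots". SAP: "Values below LLQ will be represented as LLQ/2 in the plots and in descriptive statistics".

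None of the three is tied to the pre-dose values that form the baseline. SAP 1 and SAP 12 both state that the protocol's analyses are unchanged and only detail is added.

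**The concern.** The baseline is subtracted from every corrected concentration, so an error in it carries through to corrected AUC, AUCt, Cmax, CL/F, Vz/F and half-life. FSH is suppressed on purpose; Protocol 3.5.6 gives the aim as "In order to ensure down-regulation and minimise any interference from endogenous FSH". Eligibility caps FSH at 5 IU/L and sets no lower bound, so pre-dose values below LLQ are conceivable.

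The nearby rules do not settle the matter. The zero rule applies to values already corrected, which presupposes a baseline. Exclusion leaves no baseline if all three values are below LLQ, and the SAP confines it to λz. A fixed baseline error is also a larger share of exposure at 12 µg than at 24 µg, so it tilts the dose-proportionality slope if corrected data are used. In an open-label trial the choice could be made with concentrations in view.

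Finally, the SAP replaces exclusion from the whole non-compartmental analysis (NCA) with exclusion from λz estimation, yet declares no change.

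**Working it through.** The plan gives no figure to reproduce. The check sizes the unstated choice.

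**Inputs from the documents.** Sampling at 0, every 4 h to 40 h, 48 h, then days 3 to 9 (Protocol 7.1.1); half-life 40–44 h (Protocol 3.5.1); median tmax 10–24 h (Protocol 1.1); doses 12, 18 and 24 µg, 8 women each; linear trapezoidal AUC.

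**Assumptions.** LLQ is 2, 5 or 10% of the 12 µg Cmax; constant true baseline of 0.1–0.95 LLQ; one-compartment profile with first-order absorption; exact proportionality; the SAP's zero rule applied; λz from retained samples at 72 h or later.

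**Hand check** (half-life 40 h, tmax 24 h, LLQ 5%). True AUC is 87.5 h × Cmax. Leaving LLQ/2 = 0.025 Cmax unsubtracted over 216 h adds 0.025 × 216 / 87.5 = 6.2%. With the extrapolated tail the total is 8.6%.

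**All three pre-dose values below LLQ, zero instead of LLQ/2:**

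| Assumed LLQ (% of 12 µg Cmax) | AUC, 12 µg | AUC, 24 µg | Cmax, 12 µg | Fall in AUC slope |
|---|---|---|---|---|
| 2 | +3–4% | +2% | +1% | 0.02–0.03 |
| 5 | +8–11% | +4–5% | +2.5% | 0.05–0.08 |
| 10 | +15–25% | +8–11% | +5% | 0.08–0.18 |

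The table checks itself: 10% of the 12 µg Cmax is 5% of the 24 µg Cmax, so the 24 µg entry in the last row equals the 12 µg entry in the row above. With half-life 40 h, tmax 24 h and a true baseline of LLQ/2, the fitted half-life at 12 µg under zero is 43, 47 and 51 h.

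**Precision of the slope.** The log doses deviate from their mean by −0.366, 0.039 and 0.327; the sum of squares is 0.2425, times 8 women = 1.940. At an assumed 25% CV, σ = √ln(1.0625) = 0.246. The standard error is 0.246/√1.940 = 0.177, and the 95% half-width is 2.074 × 0.177 = 0.37 (22 degrees of freedom).

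**Which convention is nearer the truth** (12 µg AUC relative to true):

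| True baseline | Rule | LLQ 2% | LLQ 5% | LLQ 10% |
|---|---|---|---|---|
| 0.1 LLQ | zero | 1.01 | 1.02 | 1.03 |
| 0.1 LLQ | LLQ/2 | 0.97–0.98 | 0.93–0.95 | 0.88–0.90 |
| 0.95 LLQ (40 h, 24 h) | zero | 1.07 | 1.17 | 1.36 |
| 0.95 LLQ (40 h, 24 h) | LLQ/2 | 1.03 | 1.08 | 1.15 |

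Zero is nearer when suppression is almost complete; LLQ/2 is nearer when the baseline lies just under LLQ.

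**Mixed values.** For pre-dose values of 0.90, 1.05 and 0.95 LLQ, the baseline is 1.05/3 = 0.35 LLQ with zero, (0.5 + 1.05 + 0.5)/3 = 0.68 LLQ with LLQ/2, and 1.05 LLQ with exclusion.

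**How often it bites.** In simulated trials of 24 women (AUC CV 25%, baseline CV 50%, assay CV 8%), zero against LLQ/2 moves the 12 µg geometric mean AUC by +3, +8 and +15% at LLQ 2, 5 and 10% if 91% of women have all three values below LLQ, and by +2, +4 and +9% if 45% do. If 5% do, it moves by +0.6% and +1.3% at LLQ 5 and 10%. If every pre-dose value is quantifiable, it does not move at all.

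**Post-dose narrowing of the exclusion.** Suppose the protocol's rule refers to measured concentrations, and take a baseline of LLQ/2. The SAP's handling then lowers the corrected 12 µg AUCt by about 0–3% at LLQ 5% and 2.5–6% at LLQ 10%. With half-life 40 h and tmax 24 h at LLQ 5% it is 83.8 against 85.2, or −1.6%. AUC to infinity is almost unchanged.

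**The case for a change.** The strongest case for a change is that single-dose pharmacokinetics is the first objective, the data support registration in China, the bias depends on dose, and one sentence written before concentrations are seen would remove the discretion. Much of the factual basis stands. No sentence assigns a rule to the baseline mean, the ratios above are right under their assumptions, and the no-change statements in SAP 1 and 12 are inaccurate on the λz point. Nor is that narrowing purely a matter of wording, because AUCt can differ by a few percent.

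Four things weaken it.

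1. The trigger is not shown. The 5 IU/L limit is checked by a local laboratory (Protocol 7.2.1), while PK samples are measured under the sponsor's bioanalysis department (Protocol 7.1.1). The cap therefore says nothing about where values fall against the PK assay's LLQ.
2. Only the λz wording replaces a protocol rule. The zero rule and the use of LLQ/2 in descriptive statistics cover matters on which the protocol is silent, and can fairly be called added detail.
3. Zero and LLQ/2 need not collide for corrected values. One reads as a calculation rule and the other as a display rule; zero cannot be drawn on the logarithmic axes that SAP 9.1 requires.
4. Open-label access adds little. There is no comparator to favour, and a single convention would naturally apply to all women.

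**Conclusion.** No change follows. This is missing detail, not a stated rule that gives a wrong result. Zero and LLQ/2 are both defensible, neither is always closer to the truth, and an analyst who meets a pre-dose value below LLQ can apply one of them throughout and say which.

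The possible effect is confined to baseline-corrected parameters: from nothing, if all pre-dose values are quantifiable, to 15–25% on the 12 µg AUC if all are below an LLQ as high as 10% of Cmax. Even then the slope moves by at most about 0.18 against a half-width of 0.37. Protocol 9.7.1 calls the trial explorative, no acceptance limits are set for proportionality, and neither document says that corrected data carry that analysis. The uncorrected NCA is reported alongside and does not use the baseline, although it includes endogenous FSH and so is a companion to the corrected analysis, not a substitute.

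The inaccurate no-change statement is a clerical slip; its numerical trace is a few percent on corrected AUCt under one reading of the protocol. All sizes rest on assumed LLQ and baseline levels and on a simple one-compartment profile.
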